6.12.7 Follow-Up Procedures

After the NB-IS TCD, TTE, SOC TCD and TEE (if performed) bubble study exams performed, the following data points will be collected:

- PFO Closure Decision (post-diagnostic procedure(s))
- Classification of Potential Causative Mechanism in PFO–Associated Stroke¹

[figure not shown]
If a PFO closure procedure is performed within 60 days post diagnostic workup, the following data points will be collected:

- PFO Closure Procedure Data
- Shunt size
- Closure device(s) used

6.13 NB-IS TCD data collection and data transfer

NB-IS TCD data will be collected and stored on the NeuralBot Investigational System. The details of the data collection and transfer can be found in the device User Manual and Data Transfer procedures.

6.14 Study workflow

7 RISKS AND BENEFITS

There is minimal potential clinical risk associated with the scans described in the study. The risks associated with the use of the NeuralBot Investigational System in humans have not been determined as this study is one of the initial uses of the device. An ongoing study utilizing the device in subjects experiencing neurological symptoms of stroke has not reported any unexpected or serious device related adverse events (Protocol No.: NA-01STR-01). The NeuralBot Investigational System is designed to be physically and electro-mechanically safe according to manufacturing standards. At any time, for any reason, the use of the device can be discontinued.

7.1 Known Potential Risks

The following device-related adverse events have been identified as possible (anticipated) with the use of the NeuralBot Investigational System:

- Physical discomfort of the head and neck due to pressure from the probe, or probe accidentally coming in contact with ears, eyes or hair.
- Psychological feeling of claustrophobia- the fear of being enclosed in a small space.

7.2 Benefits

There is no direct benefit to the subject participating in the study.

8 SAFETY ASSESSMENTS

8.1 Safety Parameters

8.1.1 Adverse Event (AE)

An adverse event (AE) is defined as any untoward medical occurrence, unintended disease or injury, or untoward clinical signs (including abnormal laboratory findings) in subjects, users, or other person, whether or not related to the investigational medical device (ISO14155:2011E).

- Note 1: This definition includes events related to the investigational medical device or the comparator
- Note 2: This definition includes events related to the procedures involved
- Note 3: For users or other persons, this definition is restricted to events related to the study device.

For the purpose of this protocol, adverse events will be reported and recorded (via eCRF) if any of the following apply:

- Causality is related to:
 - o the study device
 - the study-related procedure (not standard of care)
 - o if causality is unknown

• The event is a serious adverse event (SAE) related to the study device or study-related procedure

Any medical condition that is present at the time informed consent is obtained or prior to the start of the study procedure will be considered as baseline and not reported as an AE. Such conditions should be added to the medical history, if not previously reported.

Collection of device and/or procedure-related adverse events will start after the time that informed consent form is obtained. Device and procedure-related adverse events will be monitored throughout the study.

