4.1 Primary Efficacy Endpoint

 % detection of RLS/PFO with NB-IS TCD compared against standard of care Transthoracic Echocardiography (TTE)

4.2 Secondary Technical Efficacy Endpoints:

- % agreement for detection of RLS/PFO with NB-IS TCD vs SOC TCD
- % agreement for detection of RLS/PFO with NB-IS TCD vs Transesophageal Echocardiography (TEE)
- % agreement for detection of clinically significant shunts with NB-IS TCD vs TTE
- No window rate (including both unilateral and bilateral absent acoustic windows)
- Success rate of the NB-IS TCD
- Incidence of NB-IS device malfunctions

4.3 Exploratory Endpoints:

 Development of an automated algorithm for Spencer Logarithmic Scale¹⁰ and International Consensus Criteria grading of RLS¹¹

4.4 Primary Safety Endpoint:

Incidence of device-related serious adverse events.

4.5 Secondary Safety Endpoints:

Incidence of procedure-related adverse events related to agitated saline injection before and after VM (headache, allergic reactions, new onset neurological deficit, ischemic stroke, TIA or

DWF-C0001-001 CONFIDENTIAL Page 18 of 44

pulmonary embolism complicating agitated saline contrast injection, etc) will be closely monitored and prospectively collected¹².

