5.3 Study Entry Criteria – TTE Main Study

5.3.1 Inclusion Criteria

A subject must meet all of the following inclusions criteria to be enrolled in the study:

- 1. Subject 18 years of age and older.
- 2. Subject presents with a clinical condition characterized by neurological signs and symptoms that, in the opinion of the investigator, include embolic stroke or TIA in the differential diagnosis.
- 3. Scheduled for a transthoracic echocardiograph (TTE) study with agitated saline contrast (bubble study) within ±30 days of informed consent.
- 4. Subject is able to successfully perform a Valsalva Maneuver (VM).
- 5. Subject or Legally Authorized Representative has the ability to provide informed consent and comply with the protocol.

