6.12.3 SOC Transcranial Doppler Ultrasound Procedure (TCD) (as applicable)

If SOC TCD bubble study is performed during subject participation in the study, preference is for this exam to be conducted in same session as the NB-IS TCD with the same individual administering the bubble injections with the SOC TCD bubble exam occurring before NB-IS TCD. The SOC TCD bubble study will be performed per standard of care, however, if possible, preference would be to collect measurements similar to NB-IS TCD exam (e.g., supine position at Rest and with VM, 45 degrees at Rest and with VM, etc.).

The following data points will be collected for the SOC TCD procedure:

- SOC transcranial Doppler Ultrasound (TCD) bubble study local results (SOC)
 - Date/time of SOC TCD bubble study
 - SOC TCD scan Start/Stop times with and without VM (as applicable)
 - Saline/Air Injection(s) Start/Stop time(s) with and without VM (as applicable)
 - Head inclination (degree)/subject positioning/location of the exam
 - Local Positive/Negative results for RLS/PFO
 - Local Spencer Logarithmic Scale (SLS) grade (with and without VM)
 - Local International Consensus Criteria (ICC) grade (with and without VM)

•

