8.2 Reporting Device and/or Procedure Related Adverse Events

All suspected device related adverse events shall be recorded on the Adverse Event page of the CRF if they are suspected to be related to the use of the NeuralBot Investigational System. If appropriate, the event shall subsequently be reported to the relevant IRB. The event shall be thoroughly investigated and a causal relation as to whether the event is related or not to the use of the NeuralBot Investigational System shall be established.

The Investigator will record the nature, severity, relatedness, treatment, and outcome of the AE. This classification of the event determines the reporting procedures to be followed. NovaSignal may upgrade the classification as required for reporting purposes.

At the initiation of device use through end of use of the device, all subjects with adequate quality NeuralBot Investigational System data shall be assessed for any potentially device related complications or adverse events. All events shall be followed until resolution or through the end of a subject's study participation.

Device-related adverse events information will be collected throughout the study. From the initiation of and end of device use, all subjects scanned with the NeuralBot Investigational System shall be assessed for any potentially device related complications or adverse events. All events shall be followed until resolution or through the end of a subject's study participation.

Procedure-related adverse events related to agitated saline injection before and after VM (headache, allergic reactions, new onset neurological deficit, ischemic stroke, TIA or pulmonary embolism complicating agitated saline contrast injection, etc) will be closely monitored and prospectively collected¹⁸. Nevertheless, it should be noted that a recent multi-center study underlined the safety and importance in performing TCD-BS for RLS detection in a standardized manner using the currently recommended international consensus protocol with agitated saline intravenous injections¹⁹.

Event, onset date, severity, relatedness, device relationship, treatment and outcome of the AE will be recorded on the appropriate case report form. Any device-related and/or procedure-related AEs will be monitored until they are adequately resolved or explained. This classification of the event determines the reporting procedures to be followed. For purposes of this protocol, the following definitions will apply.

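### Section 8.1.1 makes no provision for worsening of a baseline condition, so, read literally, non-serious worsening of an existing neurological deficit after the NB-IS injections need not be reported

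*Combined protocol and SAP*

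**What the plan says.** Section 8.1.1 opens with a broad AE definition, which includes "any untoward medical occurrence, unintended disease or injury, or untoward clinical signs". It then limits what is recorded to events related to the study device or to the study-related procedure as distinct from standard of care, events of unknown causality, and SAEs related to the device or study procedure.

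A separate rule follows for conditions already present. One that exists at consent "or prior to the start of the study procedure will be considered as baseline and not reported as an AE". The only further instruction is "Such conditions should be added to the medical history, if not previously reported". Severity and frequency are not mentioned.

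The secondary safety endpoint in section 4.5 covers events related to the agitated saline injections and names "headache, allergic reactions, new onset neurological deficit, ischemic stroke, TIA or" pulmonary embolism. The same list recurs in sections 6.12.4, 8.2 and 11.8.

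For entry, criterion 2 of section 5.3.1 reads "Subject presents with a clinical condition characterized by neurological signs and symptoms", with embolic stroke or TIA in the differential diagnosis. Section 5.4.1 repeats it for the sub-study.

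**The concern.** Safety rules usually pair a baseline exclusion with a statement that worsening of a baseline condition counts as an AE. Here the second half is absent, in a population enrolled because of neurological signs and symptoms. Each subject receives four NB-IS injections of agitated saline under section 6.12.4 (rest and Valsalva, in each of two positions: 2 x 2 = 4), and neurological deficit and headache are among the harms the secondary safety endpoint exists to measure.

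If a site follows 8.1.1 to the letter, an existing deficit that becomes somewhat worse after an injection can stay in the medical history and never reach the AE page. Another site may rely on the broad definition and report it. With up to 7 centers, the reported incidence would then depend partly on how each site read the rule, and a low figure would be hard to interpret.

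**Working it through.** No figure in the plan bears on this point, so the check sets the safety texts against one another. The texts compared were the endpoint list (4.5, repeated in 6.12.4, 8.2 and 11.8), the known risks (7.1), the AE, SAE, UADE and deficiency definitions (8.1.1 to 8.1.4), the reporting and classification rules (8.2 to 8.4), the primary safety analysis (11.7), the entry criteria (5.3.1, 5.4.1) and the screening list (6.11).

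1. **Is there a worsening clause anywhere?** None of these sections states that an increase in severity or frequency of a baseline condition is an AE. None states that it is not.

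2. **What happens to each kind of event?**

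| Event after an NB-IS injection | Baseline rule, 8.1.1, read literally | Endpoint list | Section 8.1.2 | Result |
|---|---|---|---|---|
| Non-serious worsening of an existing deficit | Baseline, not reported | Not named; only new-onset deficit is | Does not apply | Need not be reported |
| Non-serious aggravation of an existing headache | Baseline, not reported | Headache named, with no requirement that it be new | Does not apply | Ambiguous |
| Serious deterioration of either | Baseline, not reported | Named only in part | Covers serious deterioration in health | Partial route |
| New stroke, TIA or deficit | Not baseline | Named | Applies if serious | Captured |

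3. **Why is the third row only partial?** The note in 8.1.2 on planned hospitalization implies that serious deterioration of a pre-existing condition can be an SAE. But 8.1.2 defines an SAE as an AE that meets further conditions. If the baseline rule takes an event out of the AEs, it is unclear how the event re-enters as an SAE.

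4. **Is there a reference against which to judge worsening?** Section 6.11 lists medical history and a standard-of-care physical examination. It specifies no record of headache or deficit status just before the first injection.

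5. **Can an undercount be sized?** Let p be the share of subjects with the condition at baseline, w their worsening rate, and n the new-event rate in the rest. If every worsening went unrecorded, the missed share would be pw / (pw + (1 - p)n). The documents give none of p, w or n. Setting w = n reduces the expression to p, so any percentage obtained that way merely returns the assumed prevalence.

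**The case against.** The best case against the point is that no sentence excludes worsening. The rule speaks of a condition being present, and an aggravation is arguably a fresh untoward occurrence under the broad definition, which expressly takes in events related to the procedures. Section 8.2 requires all scanned subjects to be assessed for potentially device-related complications. It says that the injection-related events, in a list ending "pulmonary embolism complicating agitated saline contrast injection, etc) will be closely monitored and prospectively collected", are gathered, and the list is open-ended. Events of unknown causality are reportable.

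Much of this stands. It rules out saying that worsening is not counted; the supportable statement is that it need not be. It does not close the gap for deficits: a specific exclusion in the same section can reasonably be followed over a general definition, and the endpoint wording on deficit points the same way as the exclusion.

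Four stronger readings may tempt a reader, and the documents do not support them:

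- **Standard-of-care TCD.** Section 6.12.3 prefers the two examinations in one session, "with the SOC TCD bubble exam occurring before NB-IS TCD", so a headache starting with the first set of injections seems to be lost as baseline. But events caused by standard of care are outside the reporting scope by design, and that examination is optional. Only later aggravation by the NB-IS injections matters, which is the point already made.
- **Conflicting time points.** Section 8.1.1 says "Collection of device and/or procedure-related adverse events will start after the time that informed consent form is obtained", while baseline runs to the start of the procedure. Device- or procedure-related events can hardly arise before the device or procedure is used, so this has little effect.
- **Most subjects affected.** Criterion 2 neither mentions headache nor requires a deficit that persists to the procedure. How many subjects carry either condition is unknown.
- **Serious harm off the reporting pathway.** Section 8.1.2 and its note weigh against this, and new stroke and TIA are listed in their own right.

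**Conclusion.** The point holds as a gap in the definitions. Its clearest consequence is that non-serious worsening of a pre-existing deficit after the NB-IS injections can be left out of a named safety endpoint by a site following the text. For headache the texts conflict. For serious deterioration a route exists, but its link to the baseline rule should be made explicit.

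No number can be put on the undercount. The conclusion assumes only that some subjects have a deficit or headache when the injections start, and that some sites apply 8.1.1 as written.

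It is worth correcting because it touches a safety endpoint and the correction is simple. Its reach is limited: the secondary safety endpoint carries no hypothesis, threshold or comparator; the primary efficacy endpoint is untouched; and no effect on the primary safety endpoint, device-related SAEs, has been shown.

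**What to change.** - In section 8.1.1, after the baseline rule, add: *An increase in severity or frequency of a pre-existing condition after the first study-related injection or start of device use is an AE.* This also settles the link to 8.1.2.
- In sections 4.5, 6.12.4, 8.2 and 11.8, change the deficit item to *new or worsened neurological deficit*.
- Record headache and deficit status on the eCRF immediately before the first NB-IS injection, using information already collected, as the reference for worsening.

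The cost is protocol wording and one eCRF instruction, with no added visit or procedure. The downside is that the reported AE rate may be slightly higher.

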8.1.2 Serious Adverse Event (SAE)

A serious adverse event (SAE) is defined (ISO14155:2011E) as an adverse event that:

- a) Led to a death
- b) Led to a serious deterioration in the health of the subject that:
 - 1) resulted in a life-threatening illness or injury, or
 - 2) resulted in a permanent impairment of a body structure or a body function, or
 - 3) required in-patient or prolongation of hospitalization, or
 - 4) resulted in medical or surgical intervention to prevent life-threatening illness or injury or permanent impairment to body structure or a body function
- c) Led to fetal distress, fetal death or a congenital abnormality or birth defect.

NOTE: Planned hospitalization for a pre-existing condition, or a procedure required by the protocol, without serious deterioration in health, is not considered a serious adverse event.

8.1.3 Unanticipated Adverse Device Effect (UADE/USADE)

An Unanticipated ADE (UADE) is any serious adverse effect on health or safety or any life-threatening problem or death caused by or associated with a device, if that effect, problem, or death was not previously identified in nature, severity, or degree of incidence in the protocol or application (including a supplementary plan or application (e.g., user manual, investigator's brochure, instructions for use, etc.)); or any other unanticipated serious problem associated with a device that relates to the rights, safety, or welfare of subjects (ISO14155:2011E).

8.1.4 Device Deficiency, Device Malfunction, and Use Error

Device Deficiency

Defined as inadequacy of a medical device with respect to its identity, quality, durability, reliability, safety, or performance

Device Malfunction

Defined as a failure of a medical device to perform in accordance with its intended purpose when used in accordance with the instructions for use or protocol or user manual.

Use error

Defined as the act or omission of an act that results in a different medical device response than intended by the manufacturer or expected by the user.

Note 1: Use error includes slips, lapses, and mistakes.

DWF-C0001-001 CONFIDENTIAL Page 30 of 44

Note 2: An unexpected physiological response of the subject does not in itself constitute a
use error.

Device deficiencies are also reportable if they did not lead to an adverse event but could have led to a SADE:

- a) if either suitable action had not been taken,
- b) if intervention had not been made, or
- c) if circumstances had been less fortunate

(ISO14155:2011E)

8.2 Reporting Device and/or Procedure Related Adverse Events

All suspected device related adverse events shall be recorded on the Adverse Event page of the CRF if they are suspected to be related to the use of the NeuralBot Investigational System. If appropriate, the event shall subsequently be reported to the relevant IRB. The event shall be thoroughly investigated and a causal relation as to whether the event is related or not to the use of the NeuralBot Investigational System shall be established.

The Investigator will record the nature, severity, relatedness, treatment, and outcome of the AE. This classification of the event determines the reporting procedures to be followed. NovaSignal may upgrade the classification as required for reporting purposes.

At the initiation of device use through end of use of the device, all subjects with adequate quality NeuralBot Investigational System data shall be assessed for any potentially device related complications or adverse events. All events shall be followed until resolution or through the end of a subject's study participation.

Device-related adverse events information will be collected throughout the study. From the initiation of and end of device use, all subjects scanned with the NeuralBot Investigational System shall be assessed for any potentially device related complications or adverse events. All events shall be followed until resolution or through the end of a subject's study participation.

Procedure-related adverse events related to agitated saline injection before and after VM (headache, allergic reactions, new onset neurological deficit, ischemic stroke, TIA or pulmonary embolism complicating agitated saline contrast injection, etc) will be closely monitored and prospectively collected¹⁸. Nevertheless, it should be noted that a recent multi-center study underlined the safety and importance in performing TCD-BS for RLS detection in a standardized manner using the currently recommended international consensus protocol with agitated saline intravenous injections¹⁹.

Event, onset date, severity, relatedness, device relationship, treatment and outcome of the AE will be recorded on the appropriate case report form. Any device-related and/or procedure-related AEs will be monitored until they are adequately resolved or explained. This classification of the event determines the reporting procedures to be followed. For purposes of this protocol, the following definitions will apply.

DWF-C0001-001 CONFIDENTIAL Page 31 of 44

8.3 Classification of a Device and/or Procedure Related Adverse Event

8.3.1 Severity Rating of Event

The following categories of adverse event severity are to be used:

Mild	Awareness of sign or symptom that does not interfere with the subject's usual activity or is transient, resolved without treatment and with no sequelae.
Moderate	Interferes, but does not hinder, the subject's usual activity and/or may require treatment.
Severe	Symptom(s) causing severe discomfort and significant impact on the subject's usual activity and requires treatment or intervention.

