8.4 Reporting Procedures

All UADE/SADE/SAEs must be recorded and reported to the Sponsor via the eCRFs throughout the study, *immediately upon study site staff awareness of the event but not later than 72 hours by the study site personnel.* In the event the EDC is unavailable, events can be reported via email to the Sponsor study mailbox: [contact] and/or to the study Sponsor contact. Note: The event will still need to be recorded on the eCRFs once the EDC is functional.

In case device malfunctions occur, they will be reported to NovaSignal within 10 business days. The report should include at a minimum, a description of event, date of occurrence, lot or serial number of the device.

Timing for the reporting for the different types of AEs and Device Deficiencies is described as follows:

Classification	Reporting time	Type of report
Unanticipated Adverse Device Effects (UADE)	Notify NovaSignal immediately upon study site staff awareness of event but not later than 72 hours. Notify IRB as required.	Device/Procedure Related Serious Adverse Event Report Form
Serious Adverse Events (SAE) or Serious Adverse Device Effect (SADE)	Notify NovaSignal immediately upon study site staff awareness of event but not later than 72 hours. Notify IRB as required.	Device/Procedure Related Serious Adverse Event Report Form
Study Device Deficiency/Malfunction With or Without AE	Notify NovaSignal within 10 business days of learning of event. Notify IRB as required.	Device Deficiency/ Malfunction Form

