11.8 Secondary Safety Endpoint Analysis

Throughout the study we will collect the incidence of procedure-related adverse events related to agitated saline injection before and after VM (headache, allergic reactions, new onset neurological deficit, ischemic stroke, TIA or pulmonary embolism complicating agitated saline contrast injection, etc.) will be closely monitored and prospectively collected¹⁸.

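### Section 8.3.1 allows a disabling but transient, untreated event to be graded Mild, bars it from Severe, and has no rule for overlapping grades

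*Combined protocol and SAP*

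**What the plan says.** Section 8.3.1 defines three grades.

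- Mild starts from awareness of a sign or symptom and covers one that leaves usual activity undisturbed "or is transient, resolved without treatment and with no sequelae".
- Moderate reads "Interferes, but does not hinder, the subject's usual activity and/or may require treatment".
- Severe requires symptoms that cause severe discomfort, together with "significant impact on the subject's usual activity and requires treatment or intervention".

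Nothing says which grade applies when an event meets two definitions, or what to do when it meets none.

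Section 11.8 names the procedure-related events of interest: "headache, allergic reactions, new onset neurological deficit, ischemic stroke, TIA or pulmonary embolism complicating agitated saline contrast injection". Sections 4.5, 6.12.4 and 8.2 give the same list. Section 8.2 has the event, its onset date, severity, relatedness, treatment and outcome recorded as separate items. It allows the sponsor to upgrade the classification for reporting purposes, and it states: "This classification of the event determines the reporting procedures to be followed".

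Section 8.4 introduces its table with "Timing for the reporting for the different types of AEs and Device Deficiencies is described as follows". The rows cover UADEs, SAEs or SADEs, and device deficiencies or malfunctions. Section 8.1.2 defines seriousness by consequences and does not refer to the severity grade.

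**The concern.** The scale suits the anticipated device events in section 7.1, which are discomfort from the probe and claustrophobia. It does not suit brief neurological events. Those can be disabling while they last, painless, and over before anyone treats them.

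These events matter here because the NB-IS bubble study is study-specific (section 6.10) and offers the subject no direct benefit (section 7.2). Section 6.12.4 calls for an injection at rest and one with Valsalva, first supine and then at 45 degrees, so 2 × 2 = 4 injections per subject. With up to 150 + 150 = 300 subjects, that is at most 4 × 300 = 1,200 study injections, in people who have embolic stroke or TIA in the differential diagnosis.

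Severity is the only ordered scale in section 8.3 for how bad an event was while it lasted. If the same transient deficit can be Mild at one of the up to 7 centers and Moderate at another, a tabulation by grade cannot be interpreted for the events that most need it.

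**Working it through.** The plan states no figure on this point, so the check is a logical one. Each definition is written as a condition and applied to cases.

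- Mild: no interference with usual activity, OR (transient AND resolved untreated AND no sequelae).
- Moderate: interference short of hindrance, AND/OR possible need for treatment.
- Severe: severe discomfort AND significant impact AND need for treatment or intervention.

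| Event | Mild | Moderate | Severe |
|---|---|---|---|
| 1. Transient, untreated, no sequelae, no interference (trivial headache) | met | only if judged possibly to need treatment | closed |
| 2. Same course, interferes without hindering | met by transience | met | closed |
| 3. Same course, disabling (weakness or speech loss that clears) | met by transience | only if judged possibly to need treatment | closed |
| 4. Persistent, untreated, disabling | closed | only if judged possibly to need treatment | closed |
| 5. Treated, disabling, without severe discomfort | closed | met through treatment | closed |
| 6. Treated, disabling, with severe discomfort | closed | met through treatment | met |

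Reading down the table:

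- Events 1 and 3 both qualify as Mild, although one is trivial and the other disabling.
- Severe is closed to every untreated event (1 to 4) and to every event without severe discomfort (5). A painless deficit cannot exceed Moderate even when treated.
- Events 2 and 6 meet two grades outright. Event 3 meets two if the investigator thinks treatment might have been needed.
- Event 4 has no grade if the investigator thinks treatment was not called for.

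The opening words of Mild do not remove the problem. Even if awareness of a sign or symptom governs both routes, it puts no ceiling on impact.

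Reporting is a separate check. Take a transient deficit after a study injection in a subject who is already an inpatient, with no longer stay, no intervention to prevent lasting harm, no threat to life and no permanent impairment. Section 8.1.2 need not class it as serious. Section 6.3 places subject assessment in the hospital, so this case is plausible. Section 8.1.1 still has the event entered on the eCRF as procedure-related, but no row of the section 8.4 table then gives a time limit, unless a device deficiency is also involved.

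**The case against.** The strongest case against is that this is a drafting ambiguity with little consequence. Four parts of that case stand.

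- A reader might infer that the scale forces an untreated TIA into Mild. It does not. Moderate stays open through the possible-treatment clause, and Mild also requires the absence of sequelae. The text permits Mild; it does not require it. For the same reason, a count of how many combinations of impact and course are misgraded would depend on how that clause is read, so none is offered.
- A reader might infer that a TIA becomes indistinguishable from a headache in the data. It does not. Event term, treatment and outcome are recorded separately (sections 8.2 and 8.3.3), and seriousness is judged under section 8.1.2. Section 11.8 lists event types to be collected. It does not say that they will be pooled into one figure, although it specifies no breakdown either.
- A reader might infer that safety endpoints are distorted. The primary safety endpoint counts device-related serious events and the secondary counts procedure-related events (sections 4.4 and 4.5). Neither uses the grade.
- A reader might infer that a Mild grade delays reporting. No row of section 8.4 refers to severity, so regrading alone would change no deadline. The reporting gap applies to any non-serious event without a device deficiency and is a separate point.

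Two safeguards are also fairly cited: close monitoring of these events, and the sponsor's power to upgrade. They help only in part. The upgrade is discretionary, and it works only once the sponsor knows of the event, which is what a missing deadline leaves open.

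**Conclusion.** The point holds as a defect of the scale, not as a threat to an endpoint. The written rule allows the lowest grade for a disabling transient event, withholds the highest grade from it, and leaves compliant sites free to disagree. The consequence is an unreliable severity column for the neurological events that the protocol itself singles out. The documents give no event rate, so the number of subjects affected cannot be estimated; it may be small.

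The conclusion assumes that *or* in Mild joins two sufficient routes, and that an event which cleared untreated did not require treatment in the sense of Severe. The reporting gap assumes an event that meets no criterion in section 8.1.2. An event that leads to admission or a longer stay would already fall under the 72-hour rule.

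Both changes are worth making because they are cheap and concern safety recording. Neither blocks the study.

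**What to change.** In section 8.3.1, grade by the worst functional impact reached during the event:

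- Mild: does not interfere with usual activity.
- Moderate: interferes with it, but neither prevents nor significantly limits it.
- Severe: prevents or significantly limits it.

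Remove the conditions on duration, treatment, sequelae and discomfort, and state that the highest grade met applies. Treatment and outcome keep their own fields. Section 8.2 lists an onset date but no end date; if duration is wanted, it belongs in a separate field and not in the grade.

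As a separate change to safety reporting, add TIA, new neurological deficit, ischemic stroke and pulmonary embolism related to the study procedure to the existing 72-hour row of section 8.4, whether or not they meet the SAE definition. This also gives the statement in section 8.2 about classification and reporting something to point to for these events.

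The cost is one reworded table, one added line, and a note to sites. No new visits or subjects are needed. Events already graded under the present wording would need regrading, or tabulation by the wording in force. Some events will be graded higher or reported sooner, so the safety tables may look slightly less favorable.
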